### **8.1.1 Main study parameter/endpoint**

#### ***Regulatory emotional self-efficacy – RESE***

A main advantage that is reported in qualitative studies on the use of internet-based interventions in forensic psychiatry, is that patients are working on part of their treatment independently. On top of TAU, internet-based interventions offer additional exercises and information to support the patient in dealing with their undesired aggressive behaviour. This is expected to provide them with more insights and tools to improve their aggression regulation than patients who do not follow an internet-based intervention outside of in-person treatment sessions. It is thus expected that the self-efficacy of patients that follow an additional internet-based intervention will increase more than in TAU. In other words: because they receive additional treatment via the intervention and work on it independently, their confidence in regulating their own emotions can increase.

Consequently, the primary outcome measure of this study is regulatory emotional self-efficacy. This construct is measured by means of the validated, 12-item Regulatory Emotional Self-efficacy (RESE) scale [31]. The RESE scale assesses self-efficacy in managing negative emotions (8 items) and in expressing positive emotions (4 items). Negative emotional self-efficacy refers to the perceived “capability to ameliorate negative emotional states once they are aroused in response to adversity or frustrating events and to avoid being overcome by emotions such as anger, irritation, despondency, and discouragement” [31]. Positive self-efficacy is defined as the perceived capability “to experience and to allow oneself to express positive emotions such as joy, enthusiasm and pride in response to success or pleasant events” [31]. Earlier research has demonstrated the validity and reliability of the RESE scale [31, 43, 44]. Because the RESE scale consists of only 12 items, it is easy to administer and does not require much effort of participants.

#### ***Treatment readiness – CVTRQ***

Treatment readiness refers to the presence of factors that contribute to engagement with treatment and therapeutic change [12]. This concept is often used in forensic psychiatry and does not only cover motivation and willingness to change, but also responsivity, which refers to the suitability of the treatment program offered. It incorporates internal factors such as personality and cognitive-emotional features of the patient that are related to therapeutic change. Qualitative research has shown that therapists believe that, if used well, internet-based interventions can contribute to treatment readiness because they might fit the needs and wishes of the patient, resulting in better responsivity to treatment. In other words: the use

of internet-based interventions might increase the fit between the treatment and needs of the patient, resulting in higher treatment readiness. Additionally, the patient can gain new insights and skills individually as opposed to because of a therapist, which might contribute positively to their intrinsic motivation and willingness to change [4, 5].

Treatment readiness is assessed by the Dutch version of the Corrections Victoria Treatment Readiness Questionnaire (CVTRQ): a validated self-reported questionnaire [32]. The total scale consists of 20 items, divided into four subscales. The subscale Attitude and Motivation (AM) measures attitudes and beliefs about treatment programs and the desire to change. The scale Emotional reactions (ER) measures emotional responses to the individual's offending behaviour. Offending beliefs (OB) refers to beliefs about personal responsibility for offending behaviour. The subscale Efficacy (EF) measures perceived ability to participate in treatment programs.

### ***Aggression – AVL-AV***

The main objective of forensic psychiatric treatment is to prevent (re)offending. Consequently, preventing aggression is an important goal of the entire treatment program. However, reaching this goal, even by means of long and intensive therapy has proven to be difficult. We did not select aggression as a primary outcome measure because a direct impact on changes in aggression might be too much to expect from an internet-based intervention. However, it might be that patients that the expected changes in self-efficacy due to the internet-based intervention result in actual behaviour change, so self-reported aggression is used as a secondary outcome. Self-reported aggression is assessed by means of the Dutch version of the much-used and validated Aggression Questionnaire (Aangepaste Versie van de Agressie Vragenlijst; AVL-AV) [33, 34]. The 12 items of the questionnaire are divided into four subscales: physical aggression, verbal aggression, anger, and hostility. The AVL-AV had been shown to be reliable and valid in earlier research and is easy to administer because it consists of only 12 items.

#### **8.1.2 Secondary study parameters/endpoints (if applicable)**

In order to gain more insight into if, how and why the internet-based intervention works, multiple other questionnaires are used.

### ***Risk assessment – FARE***

In treatment of all forensic psychiatric patients, risk assessment has to be conducted by means of evidence-based risk assessment instruments. In forensic psychiatric outpatient care, the Dutch standard is the Forensisch Ambulante Risico Evaluatie (FARE), version 2 [36]. The FARE is not only used to estimate the risk on recidivism, but also to monitor

changes in dynamic risk factors and risk of recidivism during treatment. Research into inter-reliability and convergent validity has shown promising results [45]. The FARE is part of Dutch guidelines on risk assessment of forensic psychiatric outpatients. According to these guidelines, the FARE is administered twice a year, i.e. once each six months.

In the FARE, 6 static and 11 dynamic risk factors are assessed. Static risk factors refer to 'unchangeable' characteristics, such as age of the first offense. While they predict the risk of recidivism, they are not changeable by means of targeted interventions. Dynamic risk factors however are more related to the individual behaviour of the person and their social and living situation. Because these 11 factors are influenceable by interventions, they will be included in the analyses of this study. The 11 evidence-based dynamic risk factors that are incorporated in the FARE are: malfunctioning on education/work; financial mismanagement; delinquent social network; limited leisure activities; problematic (former) partner relationship; instable living situation; problematic substance use; limited impulse control; malfunctional coping skills; antisocial attitude; and rule-violating behaviour.

### ***Engagement – TWEETS***

Many studies have been conducted to identify why and for whom specific internet-based interventions work. Up until now, the use of sociodemographic factors as predictors has not provided answers to these questions. Engagement is a non-specific factor that can be used to predict effectiveness of and adherence to internet-based interventions [46]. Engagement refers to the extent to which someone is involved or occupied with something, and is often related to a positive outcome, such as effectiveness. In the context of digital behaviour change interventions, engagement contains an affective, behavioural and cognitive component [46]. The affective component is focused on positive or negative feelings towards the intervention and the way in which the intervention fits with a person's identity: do people identify with the design of the technology and what it stands for? Behavioural engagement is focused on the routine that a user has regarding the use of an intervention and the extent to which it requires effort and is part of one's daily life. The cognitive component of engagement refers to the extent to which an intervention supports the user in reaching their goals and is seen as useful for their behaviour change.

In this study, engagement is measured with the TWente Engagement with Ehealth and Technologies Scale (TWEETS). The scale employs a definition of engagement that incorporates behaviour, cognition, and affect, and has been shown to have a good validity and reliability [35]. The TWEETS contains only 9 items – with three items per component of engagement - and has three slightly different versions: one for expected engagement, to be used when someone starts using an intervention, one for current engagement, to be used

during the use of an intervention, and one for past engagement, to be used when a user has completed or stopped using an intervention.

### 8.1.3 Other study parameters

To describe the characteristics of the sample, information about treatment objectives, diagnoses, age, gender, and the inpatient clinic in which they are treated will be used. These data will be retrieved at T0 from the therapist by means of a Qualtrics questionnaire. In this way, the researchers do not need access to the personal patient file.

Table 1: Overview of study parameters

Variable	Instrument	Assessment point	Invested time
Regulatory emotional self-efficacy	Regulatory Emotional Self-efficacy (RESE) scale [31]	T0, T1, T2, T3	5 min. per assessment point, 20 minutes in total
Treatment readiness	Corrections Victoria Treatment Readiness Questionnaire (CVTRQ) [32]	T0, T1, T2, T3	5 min. per assessment point, 20 minutes in total
Aggression	Aggression Questionnaire [17, 18].	T0, T1, T2, T3	5 min. per assessment point, 20 minutes in total
Risk assessment	Forensisch Ambulante Risico Evaluatie (FARE) [36]	T0 & T3*	N.a. – part of standard procedures
Engagement	TWente Engagement with Ehealth and Technologies Scale (TWEETS) [35]	T0, T1 & T2 (only in the experimental group)	5 min. per assessment point, 15 min. in total (only for experimental group)
Patients' perceived effectiveness and points of improvement	Semi-structured interviews	T2	Ca. 30 min
Therapists' perceived effectiveness and	Open-ended questionnaires (Qualtrics)	T2	Ca. 15 min

points of improvement			
-----------------------	--	--	--

*\* In this study, the FARE that is administered during the standard treatment trajectory are used to not interfere with standard procedures, meaning that the exact date of FARE administration can slightly differ from the T0 and T3 assessments.*

## **8.2 Randomisation, blinding and treatment allocation**

Because blinding is impossible due to the use of the internet-based intervention in treatment, this study is a non-blinded RCT. After a participant is screened and has given informed consent, they will be randomized by the principal investigator. The randomization will be supported by an online tool (<https://sealedenvelope.com/>). Participants are not randomized per participating organization or clinic because there are major differences in the number of patients treated by these clinics. Instead, once a patient is included, they receive a participant number, which will be aligned with a random sequence of treatment allocations, i.e. participants are either allocated to the intervention or control group. The first participant included in the study is allocated according to the first treatment allocation on the list, the second participant according to the second allocation, and so forth.

Participating therapists are informed of the group the patient is allocated to and will explain this to the patient. If a patient is randomized into the control condition, the therapist is instructed to provide treatment as usual, and can be contacted by the researcher in case a patient did not fill out questionnaires at T0, T1, T2 or T3. If a patient is randomized into the experimental group, the therapist is asked to start with the intervention 'Aggression'. Specifically, the therapist will shortly explain the goal, content and nature of the internet-based intervention and explain to the patient that they will receive one lesson per week for the next 10 weeks. Additionally, the therapist will provide written feedback on the assignments of the patients. All participating therapists are trained in the use of these types of interventions and thus know how to provide feedback. To increase the feasibility of this study and reach the intended number of participants, therapists will receive additional support from researchers to remind them to introduce the intervention. The main reason for this is that implementation research on these types of internet-based interventions in Dutch forensic outpatient care has shown that, even though therapists have the intention to use the intervention, they often forget to introduce the intervention. Additionally, if they introduced the intervention, therapists often do not mention it in their treatment sessions. Consequently, participating therapists will be regularly reminded to introduce and keep on discussing the internet-based interventions with the patients in the experimental condition.

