#### 4.4 Sample size calculation

This sample size calculation is conservatively based on the ability to detect at least a moderate effect of Cohen's  $d = .50$  on the primary outcomes at follow-up (T3). A power analysis was conducted with G\*power. The analysis was conducted with a moderate effect size of 0.5, a  $\beta$ -power of .8, a p-value of 5%, and an independent two-sided t-test as method of analysis. This analysis showed that 64 patients need to be included in each condition. This means that a total of 128 patients needs to be included. Accounting for a drop-out of 20%, the goal for inclusion is set at a total of 154 patients. It is important to note that participants in the experimental condition are considered as a 'drop-out' when they don't fill out the questionnaires at all measuring moments, not when they stop using the intervention. In other words: patients can stop using the intervention. In other words: patients can stop using the intervention, but can still complete their participation in the study if they fill out all questionnaires. Adherence to the intervention is not the same as drop-out from the study, since it is a different concept. The main reason for this is that earlier research has shown that patients often stop using these interventions before all lessons are completed, so it is not realistic to expect that all patients fully complete the intervention. In order to account for this, the number of completed lessons will be included as a moderator for effectiveness in the analyses to investigate whether adherence is related to effectiveness. Additionally, a sub-goal of this study is to determine whether engagement is a predictor of adherence and effectiveness to incorporate non-adherence to the intervention in the study. The intended 154 patients will be included at four different organizations that all have multiple forensic outpatient clinics.

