### **5.1.2 Treatment as usual**

In this study, the control group will receive treatment as usual. In general, this refers to any form of psychotherapy that is delivered by a licenced psychologist to a patient in a one-on-one setting. The main focus of treatment as usual should lie on aggression regulation. Additionally, patients should receive individual, one-on-one treatment and should not participate in group treatment of aggression during data collection.

Because this is a multi-centre study, there are minor differences between the treatment as usual for aggression between the participating clinics and even between participating therapists. To illustrate, some clinics use the 'AR op Maat' program, while others use 'Grip op Agressie' as the main guidelines for their aggression treatment. While there are minor differences in the form of these types of treatment, they are all based on the same underlying principles and models. All forms of treatment in forensic psychiatry target dynamic risk factors that have been identified by means of risk assessment instruments. In general, treatment of patients with aggressive behaviour is always focused on the improvement of self-regulation to reduce the chance of (re)offending. This is achieved by means of elements

from cognitive behavioural therapy, often combined with techniques from occupational therapy.

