#### ***Research objective 1: Self-efficacy, treatment readiness, and aggression***

To identify whether there are changes in dependent variables between the experimental and control group on baseline (T0), during the intervention (T1), post-intervention (T2) and follow-up assessment (T3), multilevel repeated-measures linear mixed models will be used. This analysis method accounts for autocorrelation within participants and missing data. Time and group will be used as fixed factors, along with their interactions, and participants are modelled as random factor. Interaction effects will be studied to identify whether the changes over time differed between groups. Main effects for time will be used to investigate whether the scores of all participants changed over time. In order to provide more insight into the main findings, Least-significant difference (LSD) post-hoc independent t-tests with Bonferroni correction will be performed to test for significant between-group differences and changes over time per group.

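### Unequal clinic size does not prevent stratifying allocation by organisation; the single list invites avoidable chance imbalance and, with no organisation term, some lost precision in single-time comparisons

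*Combined protocol and SAP*

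**What the plan says.** Section 8.2 describes one random sequence used in order of inclusion across all sites. No strata or blocks are mentioned, and one reason is given: "Participants are not randomized per participating organization or clinic because there are major differences in the number of patients treated by these clinics".

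Section 5.1.2 states that "there are minor differences between the treatment as usual for aggression between the participating clinics and even between participating therapists". Its example is that clinics follow one of two named aggression programmes. The same section expects no influence on the results, because patients are randomised.

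Section 10.1 lists the model terms for the three main outcomes: "Time and group will be used as fixed factors, along with their interactions, and participants are modelled as random factor". Neither organisation, clinic nor therapist appears in any analysis in section 10. Clinic is collected at baseline, but only to describe the sample (sections 8.1 and 8.1.3). Section 10.1 also plans post-hoc between-group tests, and section 10.2 compares the number of treatment contacts with a plain t-test.

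**The concern.** The reason given for a single list does not support the choice. Blocks within an organisation keep its arms close to equal whether it recruits 12 patients or 64. Very small clinics would leave many blocks unfilled, which argues against stratifying by clinic but not by organisation; section 4.5 expects about 38 patients in each.

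The reliance on randomisation in section 5.1.2 is incomplete. Randomisation balances sites on average, not in the one allocation that is drawn. Usual treatment is acknowledged to differ, and delivery of the module depends on the therapist's written feedback and in-session discussion (sections 5.1.1 and 8.2). A lopsided organisation therefore invites the objection that a difference reflects site mix, and the plan has no pre-specified adjustment with which to answer it.

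**Working it through.** **The plan's own figure.** Section 4.4 uses a single-time comparison: "The analysis was conducted with a moderate effect size of 0.5", "a p-value of 5%, and an independent two-sided t-test as method of analysis", power 0.80. The noncentral-t calculation gives 63.77, so 64 per arm with power 0.801, which matches "64 patients need to be included in each condition".

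**Chance imbalance.** Inputs: 154 patients (section 4.4) in four organisations of about 38 (section 4.5), taken as 39, 38, 39 and 38. The 1:1 ratio is implied by equal arms.

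- A 60:40 split or worse means 23:15 or worse out of 38, and 24:15 or worse out of 39.
- With X ~ Binomial(n, 0.5), the two-sided probabilities are 0.256 (n = 38) and 0.200 (n = 39).
- At least one of four: 1 − (1 − 0.256)² × (1 − 0.200)² = 0.65.
- A difference of 10 or more patients in at least one organisation: 42%.
- If the overall list is balanced, 200,000 simulated allocations give 46% and 25% respectively.

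**What an imbalance does to the estimate.** Suppose one organisation is split 23:15, the others offset it, and each arm has 77 patients. The organisation's share of the arms differs by 8/77 = 0.104. If its mean lies one between-organisation SD from the rest, and organisation explains 5-10% of variance (assumed), the arm difference moves by 0.104 × √0.05 = 0.023 to 0.104 × √0.10 = 0.033 SD, against a target of 0.5.

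**Precision of a single-time comparison.** If site and therapist explain a share v of the variance, the standard error without them is too large by 1/√(1 − v).

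- v = 0.05: 1/√0.95 = 1.026, or 2.6%.
- v = 0.10: 1/√0.90 = 1.054, or 5.4%.
- Power at 64 per arm with that share removed: 0.821 and 0.841, against 0.801.

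An organisation term recovers only the organisation part. In simulations of 128 patients with organisation and therapist each explaining 5-10%, power was 0.81-0.82 unadjusted and 0.82-0.84 with organisation fixed. With no organisation effect at all, the term cost about one point (0.799 to 0.787 with equal sites; 0.803 to 0.793 with unequal sites).

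**The time-by-group test.** A stable site difference raises or lowers all of a patient's scores equally. It sits in the participant intercept and cancels from change over time. In 15 simulated complete data sets (123 patients, 24 therapists, 5% of variance each for organisation and therapist), adding an organisation effect and a therapist intercept left the T3-by-group estimate identical. The mean standard error was 0.1707 in both models, with a largest difference of 0.5%. With missing T3 data, an organisation term left the result almost unchanged.

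**Type I error.** With a constant effect, the unadjusted test rejected in 5.0-5.2% of null simulations. If the effect varies by therapist, the variance ratio is f = [1 + 1 + (m − 1)ρ]/2, where m is the number of experimental patients per therapist and ρ the therapist share in that arm. Type I error is then 2[1 − Φ(1.96/√f)].

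- Worst case examined: 12 therapists, m = 64/12 = 5.33, ρ = 0.10, so f = 1.217 and type I error is 7.6%.
- Across 12 to 36 therapists and ρ from 0.01 to 0.10, the range is 5.0-7.6%.
- An organisation term does not repair this: 5.9-7.4% in simulation, against 5.7-7.0% without it.

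**The case against.** The other side is right on several points, and they limit the claim.

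- **Validity.** A reader might infer that ignoring site biases the comparison or makes the test anti-conservative. The design does not support that. Patients are randomised individually, the ordinary standard error already allows for chance imbalance, and a typical imbalance moves the estimate by only 0.02-0.03 SD.
- **The main model.** A reader might also infer that site and therapist variance inflates the error of the time-by-group test. It does not, because stable differences cancel. Only sites that differ in change over time would matter there, and those call for an organisation-by-time term.
- **Programme.** Section 5.1.2 says that the programmes differ by clinic, not by organisation. Stratifying by organisation need not balance them.
- **Size.** The documents give no intraclass correlation, describe the differences as minor and expect no major differences in outcome. The 5-10% share is an assumption.
- **Predictability.** The trial is open and the principal investigator randomises, so blocks within an organisation are easier to guess than one list across four.

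None of this rescues the stated reason for not stratifying, or supplies an adjustment if a reader challenges the site mix.

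**Conclusion.** The point holds as one of avoidable imbalance and modest precision. A 60:40 split or worse in at least one organisation is about as likely as not (46%) if the overall list is balanced, and more likely than not (65%) under simple randomisation. Both figures assume about 38 patients each; section 8.2 does not say which kind of list is used.

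The 2.6-5.4% excess in the standard error rests on the assumed 5-10% variance share. It applies to the post-hoc between-group tests in section 10.1 and the treatment-contacts t-test in section 10.2, not to the time-by-group test. Type I error is at risk only if the effect varies by therapist. That is plausible given how the module is delivered, but nothing in the documents quantifies it, and a therapist intercept alone would not address it.

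**What to change.** 1. **Allocation (section 8.2).** Generate the list in the same online tool with permuted blocks of varying size, stratified by the four organisations and not by clinic. Replace the sentence on unequal size.
2. **Models (sections 10.1 and 10.2).** Include organisation as a fixed effect, with organisation by time if sites may differ in change. Replace the plain t-test on treatment contacts with a comparison adjusted for organisation.
3. **Therapist.** Record the therapist for each patient; the documents describe no such field. Add a therapist-by-group random effect as a sensitivity analysis.

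If recruitment has begun, leave the list alone and make only the analysis changes, before outcomes are seen by arm.

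The cost is a new list, one data field and a few lines of analysis text. Organisation uses 4 − 1 = 3 degrees of freedom, and organisation by time a further 3 × 3 = 9. The downside is slight predictability at block ends in an open trial, limited by varying the block size and keeping the sizes from those who enrol.
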